10.3.1 Clinically notable laboratory values and vital signs

Clinically notable laboratory abnormalities for selected tests performed by Central Laboratory (based on: 1) proportional or absolute changes from baseline; 2) the limit of the normal range established by the Central Laboratory; 3) cut-off values used to define Grade 3 as established by the Common Terminology Criteria for Adverse Events [CTCAE] (CTCAE) v 5.0 or higher)

Hematology

Table 10-1 Clinically notable hematology abnormalities

Parameter	Shift	Criteria	
Red blood cell count	Increase	> 50% increase AND value > ULN	
	Decrease	> 30% decrease AND value < LLN	
Hemoglobin	Increase	> 50% increase AND value > ULN	
	Decrease	either (> 30% decrease AND value < LLN) OR value < 8.0 g/dL	
Hematocrit	Increase	> 50% increase AND value > ULN	
	Decrease	> 30% decrease AND value < LLN	
White blood cell count	Increase	value > 100,000 cells/mm ³	
	Decrease	value < 2000 cells/mm ³	
Platelet count Decrease value < 50,000 platelets/mm ³		value < 50,000 platelets/mm ³	
ULN: upper limit of the normal range; LLN: lower limit of the normal range			

Blood chemistry

Table 10-2 Clinically notable blood chemistry abnormalities

Parameter	Shift	Criteria	
n		value > 5 x ULN if baseline was normal OR value > 5 x baseline if baseline was abnormally high.	
ALT (SGPT)	Increase	value > 5 x ULN if baseline was normal OR value > 5 x baseline if baseline was abnormally high.	
AST (SGOT)	Increase	value > 5 x ULN if baseline was normal OR value > 5 x baseline if baseline was abnormally high.	
Total bilirubin	Increase	value > 3 x ULN if baseline was normal OR value > 3 x baseline if baseline was abnormally high.	
BUN	Increase	≥ 50% increase	
Creatinine	Increase	≥ 50% increase	
Potassium	Increase	value > 6.0 mmol/L	
	Decrease	value < 3.0 mmol/L	
Chloride	Increase	> 115 mEq/L	
	Decrease	< 90 mEq/L	

Parameter	Shift	Criteria
Calcium	Increase	corrected serum calcium > 3.1 mmol/L
	Decrease	corrected serum calcium < 1.75 mmol/L
Uric acid	Increase	> 50% increase
Plasma glucose	Increase	> 25% increase
	Decrease	value < 40 mg/dL
ULN: upper limit of the nor	mal range	

Along with investigators, the clinical trial team from Novartis will receive alerts for clinically notable values via fax/e-portal (or appropriate means agreed with central labs and Novartis).

10.4 Appendix 4: Participant Engagement

Not applicable.

10.5 Appendix 5: Liver safety monitoring

10.5.1 Liver event and laboratory trigger definitions & follow-up requirements

Table 10-3 Liver event and laboratory trigger definitions

	Definition/ threshold
If ALT or AST normal at baseline	
Liver laboratory triggers	· 3 x ULN < ALT or AST ≤ 5 x ULN
	· TBL > ULN*
Liver events	· ALT or AST > 5 × ULN
	· ALP > 2 × ULN (in the absence of known bone
	pathology)
	· Total bilirubin > 3 × ULN (in the absence of known Gilbert syndrome)
	· ALT or AST > 3 × ULN AND (TBL > 2 x ULN OR INR >
	1.5)
	· Potential Hy's Law cases (defined as ALT or AST > 3
	× ULN and Total bilirubin > 2 × ULN [mainly conjugated
	fraction] without notable increase in ALP to > 2 ×
	ULN)†
	· Any clinical event of jaundice (or equivalent term) · ALT or AST > 3 × ULN accompanied by (general)
	malaise, fatigue, abdominal pain, nausea, or vomiting,
	or rash with eosinophilia
	· Any adverse event potentially indicative of a liver
	toxicity
If ALT or AST elevated at baseline:	
Liver laboratory triggers	· ALT or AST > 2 x baseline or > 200 U/L (whichever
	occurs first) · TBL > ULN*
Liver events	· ALT or AST > 3 x baseline or > 300 U/L (whichever
Liver events	occurs first)
	· (ALT or AST > 2 × baseline or > 200 U/L [whichever
	occurs first]) AND (TBL > 2 x ULN OR INR > 1.5)
	\cdot ALT or AST > 5 × ULN
	· ALP > 2 × ULN (in the absence of known bone
	pathology)
	· Total bilirubin > 3 × ULN (in the absence of known Gilbert syndrome)
	· Potential Hy's Law cases (defined as ALT or AST > 3
	× ULN and Total bilirubin > 2 × ULN [mainly conjugated
	fraction] without notable increase in ALP to > 2 × ULN)
	· Any clinical event of jaundice (or equivalent term)
	· (ALT or AST > 2 × baseline or > 200 U/L [whichever
	occurs first]) accompanied by (general) malaise, fatigue, abdominal pain, nausea, or vomiting, or rash
	with eosinophilia
	· Any adverse event potentially indicative of a liver
	toxicity
* Fractionate bilirubin, evaluate for cholestation	c liver injury (ALP) or alternative causes of bilirubin elevation. Treat

^{*} Fractionate bilirubin, evaluate for cholestatic liver injury (ALP) or alternative causes of bilirubin elevation. Treat alternative causes according to local institutional guidelines

[†] Please, consult Section 8.6.2 on reporting requirements of potential Hy's Law cases

Table 10-4 Follow-up requirements for liver triggers (based on ALT, AST and TBL values)

values)				
	ALT	TBL	Liver Symptoms	Action
ALT increase without bilirubin increase:				
	If normal at baseline: ALT > 3 x ULN	Normal For participants with	None · No change to study treatment	
	If elevated at baseline: ALT > 2 x baseline or > 200 U/L (whichever occurs first)	Gilbert's syndrome: No change in baseline TBL CK, a 48-72 Follo	AST, ALP, GGT, TBIL, INR, albumin, CK, and GLDH in 48-72 hours. • Follow-up for symptoms.	
	If normal at baseline: ALT > 5 x ULN for more than two weeks	Normal For participants with Gilbert's syndrome: No change in	None	· Interrupt study drug · Measure ALT, AST, ALP, GGT, TBIL, INR, albumin,
	If elevated at baseline:	baseline TBL		CK, and GLDH in 48-72 hours.
	ALT > 3 x baseline or > 300 U/L (whichever occurs first) for more than two weeks			Follow-up for symptoms. Initiate close monitoring and workup for
	If normal at baseline:	Normal	None	competing etiologies. · Study drug can be
	ALT > 8 x ULN			restarted only if
ALT increase with b	ilirubin increase:	_		another etiology is
	If normal at baseline:	TBL > 2 x ULN (or INR > 1.5)	None	identified and liver enzymes return to baseline.
	ALT > 3 x ULN	For participants		
	If elevated at baseline:	with Gilbert's syndrome: Doubling of direct		
	ALT > 2 x baseline or > 200 U/L (whichever occurs first)	bilirubin		
	If normal at baseline:	Normal or elevated	Severe fatigue, nausea, vomiting,	
	ALT > 3 x ULN		right upper quadrant pain	
	If elevated at baseline:		quaurani pain	
	ALT > 2 x baseline or > 200 U/L (whichever occurs first)			

Table 10-5 Follow-up requirements for liver laboratory triggers based on isolated elevations in TBL

Criterion	Actions required	Follow-up monitoring
Total Bilirubin (isolated)		
Any elevation > ULN	Fractionate bilirubin, evaluate for cholestatic liver injury (ALP) or alternative causes of bilirubin elevation. Treat alternative causes according to local institutional guidelines	As shown below according to the degree of elevation
>1.5 – 3.0 x ULN	Maintain treatment Repeat LFTs within 48-72 hours	Monitor LFTs weekly until resolution to ≤ Grade 1 or to baseline
> 3 - 10 × ULN (in the absence of known Gilbert syndrome)	Interrupt treatment Repeat LFT within 48-72 hours Hospitalize if clinically appropriate Establish causality Record the AE and contributing factors (e.g. concomitant medications, medical history, lab test) in the appropriate CRF	Monitor LFTs weekly until resolution to ≤ Grade 1 or to baseline (ALT, AST, total bilirubin, Alb, PT/INR, ALP and GGT) Test for hemolysis (e.g. reticulocytes, haptoglobin, unconjugated [indirect] bilirubin)
> 10 x ULN	· Discontinue the study treatment immediately after all other alternative causes are ruled out · Record the AE and contributing factors (e.g. concomitant medications, medical history, lab test) in the appropriate CRF	Monitor ALT, AST, total bilirubin, Alb, PT/INR, ALP and GGT until resolution (frequency at investigator discretion)
Any AE potentially indicative of a liver toxicity	Consider study treatment interruption or discontinuation Hospitalization if clinically appropriate Establish causality Record the AE and contributing factors(e.g., conmeds, med hx, lab)in the appropriate CRF	Investigator discretion

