8.4.6 Other safety evaluations

8.4.6.1 Liver safety monitoring

To ensure participant safety and enhance reliability in determining the hepatotoxic potential of an investigational drug, a standardized process for identification, monitoring and evaluation of liver events has to be followed.

Please refer to Table 10-1 and Table 10-3 in Section 10.5.1 for complete definitions of liver laboratory triggers.

Once a participant is exposed to study treatment, every liver event defined in Table 10-3 and Table 10-5 should be followed up by the investigator or designated personnel at the trial site, as summarized below. Additional details on actions required in case of liver events are outlined in Table 10-4 and Table 10-5. Repeat liver chemistry tests (i.e., ALT, AST, total bilirubin (TBL), PT/INR, Alkaline phosphatase [ALP] and GGT) to confirm elevation.

These liver chemistry repeats will be performed using the central laboratory. If results will not be available from the central laboratory, then the repeats can also be performed at a local laboratory to monitor the safety of the participant. If a liver event is subsequently reported, any local liver chemistry tests previously conducted that are associated with this event should have results recorded on the appropriate CRF.

If the initial elevation is confirmed, close observation of the participant will be initiated, including consideration of treatment interruption if deemed appropriate.

If a liver AE is reported that corresponds to these liver events, an assessment of the causal role of each study medication in the origin of the liver AE must be provided.

The following actions should be considered:

- Discontinuation of the investigational drug (refer to the Discontinuation of study treatment, Section 7.1), if appropriate
- Hospitalization of the participant if appropriate

As well, the follow-up actions described in Section 6.5.4.1 should be performed. All follow-up information and findings from consultations and procedures must be recorded as appropriate in the CRFs.

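### Liver events are defined on ALT or AST, but the table of required study-drug actions names ALT only, so an event carried by AST alone meets no row of it

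*Protocol*

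**What the plan says.** **Definitions.** Protocol Table 10-3 accepts either enzyme throughout. For a participant with normal baseline values the laboratory trigger is "3 x ULN < ALT or AST ≤ 5 x ULN" and one of the liver events is "ALT or AST > 5 × ULN". Section 6.5.4.1 (potential DILI) and Section 8.6.2 (potential Hy's Law) are likewise worded for either enzyme.

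**Actions.** Section 8.4.6.1 states that "every liver event defined in Table 10-3 and Table 10-5 should be followed up by the investigator" and points to Tables 10-4 and 10-5 for the actions required. Table 10-4 is titled "Follow-up requirements for liver triggers (based on ALT, AST and TBL values". Its first enzyme column is headed ALT, its first row group is "ALT increase without bilirubin increase", and a typical threshold is "ALT > 5 x ULN for more than two weeks", with the action "Interrupt study drug".

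**Status of the actions.** Section 6.5.3 names Appendix 5 as the place for the liver-related interruption and discontinuation criteria, and does not allow deviation from mandatory interruptions. Section 7.1 requires discontinuation for an unacceptable safety risk and refers to Section 10.5 for liver events.

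**Bilirubin.** Table 10-5 interrupts treatment for isolated total bilirubin >3-10 x ULN in the absence of known Gilbert syndrome. For >10 x ULN its study-drug instruction is "Discontinue the study treatment immediately after all other alternative causes are ruled out".

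**The concern.** The table that defines an event and the table that says what to do about it should use the same criteria. Here a participant can satisfy the first and match nothing in the second, depending on which transaminase rises. The title of Table 10-4 says that AST is covered, so a site could reasonably read AST into the rows, while another site applies the rows as printed. Two sites could then handle the same result differently under criteria that the protocol treats as binding.

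The practical setting is narrow but real. Study drug is given as three clinic injections (baseline, Week 4, Week 8), with safety laboratory tests at Weeks 2, 4 and 8. The tables therefore bear on whether the next injection of a long-acting antibody is given. Because treatment discontinuation is an intercurrent event, divergent reading could also reach the efficacy data.

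**Working it through.** No sample size, power or alpha figure is involved. The check is a reading of the tables side by side, with counts.

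**1. Which enzymes define an event (Table 10-3).**
- Normal baseline, 5 transaminase criteria: the trigger; the >5 x ULN event; >3 x ULN with TBL >2 x ULN or INR >1.5; potential Hy's Law; >3 x ULN with symptoms.
- Elevated baseline, 6 criteria: the trigger; the >3 x baseline or >300 U/L event; the combination with TBL or INR; >5 x ULN; potential Hy's Law; the combination with symptoms.
- Total 5 + 6 = 11. All 11 accept ALT or AST.

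**2. Which enzymes select an action (Table 10-4).**

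| Row | Transaminase thresholds (normal + elevated baseline) | Enzyme named | Study-drug action |
|---|---|---|---|
| Lowest ALT band, bilirubin normal | 2 | ALT | No change |
| Higher ALT band lasting over two weeks | 2 | ALT | Interrupt |
| >8 x ULN | 1 | ALT | Interrupt |
| With raised TBL or INR | 2 | ALT | Interrupt |
| With symptoms | 2 | ALT | Interrupt |

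Thresholds: 2 + 2 + 1 + 2 + 2 = 9, of which 9 name ALT and 0 name AST. AST appears in the table only among the tests to repeat. Four of the five rows carry an interruption. The tables were read from PDF, but the ALT-only wording recurs in the column head, the group heads and every threshold, so a lost cell is an unlikely explanation.

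**3. One case traced through.** Take normal baseline, AST >3 x ULN, TBL >2 x ULN and ALT at or below 3 x ULN.
- Table 10-3: a liver event, and possibly a Hy's Law case depending on ALP and bilirubin fraction.
- Table 10-4: for normal baseline the lowest ALT threshold in any row is >3 x ULN, so no row is met.
- Table 10-5: written for isolated bilirubin elevations, so its graded rows do not address this case. Its last row, for any adverse event suggesting liver toxicity, asks the investigator to consider interruption or discontinuation.
- Section 8.4.6.1: repeat tests, close observation if confirmed, and consideration of interruption or discontinuation.
- Sections 6.5.4.1 and 8.6.2: work-up, and prompt SAE reporting of a potential Hy's Law case.
- Section 7.1: discontinuation if the risk is judged unacceptable.

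Everything except an explicit study-drug action is supplied.

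**4. The two upper bilirubin bands (Table 10-5).** At >3-10 x ULN interruption is listed with no precondition. At >10 x ULN discontinuation is listed with one precondition, a completed rule-out of other causes. That row does not say whether study drug is held during the work-up, and the table gives no times for either stop.

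**The case against.** The strongest reply is that AST-only events are far from unmanaged. Section 7.1 obliges the investigator to stop treatment that would harm the participant. The case traced above is also the one best served by the rest of the protocol, since Sections 6.5.4.1, 8.4.6.1 and 8.6.2 all apply to it. This stands. A reader might infer that an AST-carried event goes without follow-up or cannot lead to stopping; the documents do not support that. What remains is that each route to stopping rests on judgement, and Section 7.1 refers back to Section 10.5 for liver events, where the explicit action table omits AST.

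A reader might also infer that every row of Table 10-4 withholds an interruption from AST-only events. That is too strong, because the first row leaves treatment unchanged.

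On bilirubin, a reader might infer that the more severe finding gets the slower stop, or no immediate action. The table does not say so. It gives no times, and the two actions differ in kind: an interruption against a discontinuation. The row for any elevation above ULN already calls for fractionation and evaluation of causes, and the >10 x ULN row adds recording and monitoring. Absent known Gilbert syndrome, such a value is also a Table 10-3 liver event. What stands is the silence on study drug while the work-up runs.

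Finally, with injections four weeks apart and drug possibly detectable for about 90 days, the gap affects dosing only when an injection falls due during the event. That limits the consequence without removing the contradiction.

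**Conclusion.** The contradiction holds on the current text. Table 10-4 disagrees with its own title and with the event definitions it is meant to serve: 11 of 11 defining criteria accept either enzyme, and 0 of 9 action thresholds name AST. The consequence is limited to the absence of an explicit study-drug action for AST-only events, in a table where four of five rows interrupt. The bilirubin point is secondary and concerns an unstated step.

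A reader might infer that all efficacy estimands are materially affected. The documents do not support this. The primary and first two secondary estimands use a treatment policy strategy, so data after discontinuation are kept. The main route is the composite BP-control endpoint, where discontinuation counts as failure, and Section 7.1 defines discontinuation as a permanent stop, so a temporary hold does not count. The documents give no expected frequency of AST-only events, so the effect cannot be quantified; a small one is likely. Sample size, power and alpha are untouched. The point deserves correction because it concerns safety criteria presented as mandatory. No view is taken on which threshold or action is right.

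**What to change.** The sponsor's safety team should:

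1. Reconcile Table 10-4 with its title and with Table 10-3.
2. Reconcile the >3-10 and >10 x ULN rows of Table 10-5, so that the handling of study drug during the work-up is stated.
3. Cite the reconciled tables consistently from Sections 6.5.3, 7.1 and 8.4.6.1. Two cross-references need attention at the same time: Section 6.5.3 says interruptions are not permitted before referring to Appendix 5 for interruption criteria, and Section 8.4.6.1 cites Table 10-1, a hematology table, for liver triggers.

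The clinical content is for the safety team to decide. The cost is wording in two appendix tables and a few cross-references, made through a protocol amendment as Section 10.1.8.1 requires. No new data are needed, since AST is already in both the full and the abbreviated laboratory panels (Table 8-2).

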10.6 Appendix 6: Renal safety monitoring

10.6.1 Specific Renal Alert Criteria and Actions and Event Follow-up

Table 10-6 Renal event criteria and corresponding actions to be taken upon their occurrence

Renal event	Actions
Confirmed serum creatinine increase of	Consider causes and possible interventions
25 – 49% from baseline	Follow-up within 2-5 days
Confirmed serum creatinine increase ≥ 50% from	Consider causes and possible interventions
baseline (corresponds to KDIGO criterion for acute	Repeat assessment within 24-48h if possible
kidney injury)	Consider drug interruption or
	discontinuation unless other causes are
	diagnosed and corrected
	Consider participant hospitalization
	and specialized treatment
New onset dipstick proteinuria ≥ 300 mg/dl	Consider causes and possible interventions
OR	Assess serum albumin and serum total protein
Protein-creatinine ratio (PCR) ≥ 1g/g Cr (or mg/mmol	Repeat assessment to confirm
equivalent as converted by the measuring laboratory)	Consider drug interruption or discontinuation
	unless other causes are diagnosed and corrected
New onset of hematuria ≥ 1 mg/dl on urine dipstick	Repeat assessment to confirm
	Distinguish hemoglobinuria from hematuria
	Urine sediment microscopy
	Assess serum creatinine
	Exclude infection, trauma, bleeding from the
	distal urinary tract or bladder, menstruation
	Consider bleeding disorder

FOLLOW-UP OF RENAL EVENTS

Assess, document and record in CRF:

- Urine dipstick and sediment microscopy evidence of drug-induced nephrotoxicity (DIN): crystals, red blood cells (dysmorphic/glomerular vs. non-dysmorphic/non-glomerular), white blood cells, tubular epithelial cells
- Blood pressure and body weight
- Serum creatinine, BUN, electrolytes (sodium, potassium, phosphate, calcium), bicarbonate and uric acid
- Urine output

Review and record possible contributing factors to the renal event (co-medications, other co-morbid conditions) and additional diagnostic procedures (MRI etc.) in the CRF

[figure not shown]
Monitor participant regularly (frequency at investigator's discretion) until:

• Event resolution: (sCr within 10% of baseline or PCR < 1 g/g Cr, or ACR <300 mg/g Cr)

or

- Event stabilization: sCr level with $\pm 10\%$ variability over last 6 months or protein-creatinine ratio stabilization at a new level with $\pm 50\%$ variability over last 6 months.
- Analysis of urine markers in samples collected over the course of the DIN event

10.7 Appendix 7: Managing hypotension

As a general guidance the following events require action:

Persistent symptomatic hypotension regardless of blood pressure readings

Ensure the participant's hydration status is adequate and that there is no other clinical reason for hypotension that may need attention.

If appropriate, adjust any non background antihypertensive concomitant medications potentially contributing to hypotension (e.g., tricyclics, hypnotic sedatives, beta blockers for non-CV disorders, etc.) and increase sodium intake by favoring salty foods.

If the above interventions do not resolve the hypotension AE, adjust the doses of one or more background medicines as necessary depending on participant's tolerability profile and laboratory assessments. Investigator should exercise best clinical judgement based on laboratory assessments, volume status and any other clinical considerations in individual subjects.

If hypotension persists and no further action can be taken with background therapy, the study

drug should be withdrawn. No down titration of study drug dose is allowed.

XXB may increase the risk of prolonged hypotension in case of acute hemorrhage or hypovolemia. Subjects should be managed with appropriate fluid replacement and should be carefully monitored for hemodynamic stability. There is no antidote to XXB available at this time. Diuretics, RAS blockers, and CCBs may be stopped and resumed when hypotension is resolved.

10.8 Appendix 8: Recommended minimum doses of background medication

Table 10-7, Table 10-8, Table 10-9, Table 10-10 list the minimum doses of commonly prescribed thiazide/thiazide-like diuretics, long-acting dihydropyridine CCBs, ACEIs, and ARBs the participant is recommended be on.

If the participant is not receiving the maximum dose per locally approved label and/or treatment guideline, the reason for that must be properly documented in the participant's eCRF.

Table 10-7 Thiazide or thiazide-like diuretics

Medication name	Minimum daily dose
Chlorthalidone	12.5 mg
Hydrochlorothiazide	25 mg
Metolazone	2.5 mg (or 0.5 mg SR)
Indapamide	2.5 mg (or 1.25 mg XL)
Bendroflumethiazide	2.5 mg
Hydroflumethiazide	25 mg
Trichlormethiazide	2 mg
Xipamide	20 mg

Potassium sparing diuretics (excluding MRAs such as spironolactone and eplerenone) either in combination or in addition to Thiazide / thiazide like diuretics are allowed.

Table 10-8 Long-acting dihydropyridine calcium channel blockers (CCBs)

Drug name	Minimum daily dose
Amlodipine	5 mg
Nifedipine (extended release)	60 mg
Felodipine (extended release)	5 mg
Lercanidipine	20 mg
Nitrendipine	20 mg OD (long acting)

Table 10-9 Angiotensin converting enzyme inhibitors

Drug name	Minimum daily dose
Benazepril	20 mg
Captopril	100 mg (50 mg BID)
Cilazapril	5 mg
Enalapril	20 mg
Fosinopril	40 mg
Imidapril	10 mg
Lisinopril	20 mg
Moxepril	15 mg
Perindopril	4 mg
Quinapril	20 mg
Ramipril	10 mg
Trandolapril	4 mg
Zofenopril	60 mg

Table 10-10 Angiotensin receptor blockers

Drug name	Minimum daily dose
Losartan	100 mg
Candesartan	16 mg
Eprosartan	600 mg
Irbesartan	150 mg
Telmisartan	40 mg
Olmesartan	20 mg
Azilsartan medoximil	40 mg
Valsartan	160 mg

11 References

References are available upon request

